#### **Principal Analyses**

MBS freedom outcomes at 2 hours post-dose will be summarized by treatment group (see Section 6.3.5.2). Outcomes will be summarized analogously for each subgroup level of all efficacy subgroups of interest specified in Section 6.1.3 plus MBS at on-study migraine attack onset (nausea, phonophobia, photophobia).

The percentages of subjects with MBS freedom at 2 hours post-dose will be compared pairwise between each BHV-3500 treatment group and placebo using CMH tests stratified by prophylactic migraine medication use at randomization (yes, no). In these analyses, the NC=F and RM=F methods will be applied. The same statistics will be presented as those for the principal analysis of pain freedom at 2 hours post-dose (see Section 6.3.3.1). The stratified percentage difference between each BHV-3500 treatment group and placebo will be tested at a Bonferroni-corrected alpha level of 0.0167. A BHV-3500 treatment group will be considered to be superior to placebo for this co-primary endpoint if the p-value for the stratified percentage difference is < 0.0167.

The principal analysis will be repeated unstratified for each subgroup level of all efficacy subgroups of interest specified in Section 6.1.3 plus MBS at on-study migraine attack onset (nausea, phonophobia, photophobia).

# **Sensitivity Analyses**

Sensitivity analyses will include the following:

- Complete cases: The principal analysis will be repeated using NC=M, i.e., subjects who have missing MBS status in the 2-hour post-dose analysis window are excluded. First, subjects whose MBS at on-study migraine attack onset is missing will be classified as failures. Next, the RM=F method of handling intervening rescue medication use will be applied. Finally, subjects with missing data in the 2-hour post-dose analysis window will be excluded.
- Multiple imputation: The principal analysis will be repeated using the copy from reference multiple imputation approach with m=20 imputations to impute missing MBS status in the 2-hour post-dose analysis window. First, subjects whose MBS at on-study migraine attack onset is missing will be classified as failures. Next, the RM=F method of handling intervening rescue medication use will be applied. Finally, missing data in the 2-hour post-dose analysis window will be imputed.
- Varying response rate imputation: The principal analysis will be repeated by imputing missing MBS at 2 hours post-dose in each treatment group with varying response rates over the range of 0%, 10%, 20% and 30%. First, subjects whose MBS at on-study migraine attack onset is missing will be classified as failures. Next, the RM=F method of handling intervening rescue medication use will be applied. Finally, missing data in the 2-hour post-dose analysis window will be imputed.

See Section 6.3.3.1 for additional details about methods and the presentation of statistics.

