#### 5 SAMPLE SIZE AND POWER

If 95% of the 400 subjects randomized to each treatment group treat a migraine on study, then there will be roughly 380 mITT subjects in each treatment group.

If the true response rates for pain freedom at 2 hours are 22% and 12% in the BHV-3500 and placebo groups, then a chi-square test at alpha=0.0167 will have 90% power. Similarly, if the true response rates for MBS freedom at 2 hours are 45% and 32% in the BHV-3500 and placebo groups, then a chi-square test at alpha=0.0167 will have 90% power. Under the assumption that the endpoints are independent, the power for both endpoints jointly is roughly 80%.

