#### **Sensitivity Analyses**

Sensitivity analyses will include the following:

- Complete cases: The principal analysis will be repeated using NC=M, i.e., subjects who have missing pain level in the 2-hour post-dose analysis window are excluded. First, the RM=F method of handling intervening rescue medication use will be applied. Next, subjects with missing data in the 2-hour analysis window will be excluded. The same statistics as the principal analysis will be presented.
- Multiple imputation: The principal analysis will be repeated using the copy from reference multiple imputation approach with m=20 imputations to impute missing pain data at 2 hours post-dose. The fully conditional specification (FCS) method is used with a generalized logit distribution. Covariates may include prophylactic migraine medication use at randomization (yes or no), sex, pain level at on-study migraine attack onset (moderate or severe), historical number of moderate to severe migraine attacks per month (< median, ≥ median), and MBS at on-study migraine attack onset (nausea, phonophobia, or photophobia). First, the RM=F

method of handling intervening rescue medication use will be applied. Next, missing data in the 2-hour post-dose analysis window will be imputed for subjects who are not missing any of the covariates (subjects missing any of the covariates will be considered failures). The same statistics as the principal analysis will be presented.

• Varying response rate imputation: The principal analysis will be repeated by imputing missing pain data at 2 hours post-dose in each treatment group with varying response rates over the range of 0%, 10%, 20% and 30%. First, the RM=F method of handling intervening rescue medication use will be applied. Next, missing data in the 2-hour post-dose analysis window will be imputed. The following statistics will be presented: stratified percentage difference between treatment groups (BHV-3500 – placebo), ASE, 98.3% CI, and p-value.

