### 7 CONVENTIONS

#### 7.1 General

### 7.1.1 Output Layout

All programmed outputs (i.e., TLFs) will be formatted and numbered according to the latest version of Biohaven Standard Outputs for CSRs.

A list of TLFs and corresponding templates will be presented separately in a mock TLF document corresponding to this SAP.

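### The varying-response-rate sensitivity analysis does not say whether active and placebo imputed rates are crossed, and its 30% maximum lies below both planning rates for MBS freedom

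*SAP*

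**What the plan says.** SAP 6.3.3.2 (MBS freedom, Sensitivity Analyses) repeats the principal analysis by "imputing missing MBS at 2 hours post-dose in each treatment group with varying response rates over the range of 0%, 10%, 20% and 30"%. SAP 6.3.3.1 does the same for "missing pain data at 2 hours post-dose in each treatment group with varying response rates over the range of 0%, 10%, 20% and 30"%. The MBS section refers back to 6.3.3.1 for method. There the text adds only the order of steps (rescue use classed as failure first, imputation second) and the statistics to be shown. Neither section states how the rate in one arm relates to the rate in the other.

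SAP Section 5 plans on the basis that "true response rates for pain freedom at 2 hours are 22% and 12% in the BHV-3500 and placebo groups", and "if the true response rates for MBS freedom at 2 hours are 45% and 32% in the BHV-3500 and placebo groups".

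Two other sensitivity analyses are planned for MBS freedom. In the complete-case analysis, "subjects who have missing MBS status in the 2-hour post-dose analysis window are excluded". The other uses the "copy from reference multiple imputation approach with m=20 imputations to impute missing MBS status". The principal analysis counts missing 2-hour data as failure (NC=F), and a dose is declared "superior to placebo for this co-primary endpoint if the p-value for the stratified percentage difference is < 0.0167".

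On table layout, SAP 7.1.1 says "A list of TLFs and corresponding templates will be presented separately in a mock TLF document corresponding to this SAP".

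**The concern.** The most informative challenge to a significant result is to let missing active subjects respond less often than missing placebo subjects. The imputation wording allows two readings. Under one, a single rate is applied to all arms, giving four results per dose. Under the other, every active rate is paired with every placebo rate, giving 4 x 4 = 16 results per dose. Only the second contains the challenging cells. Two programmers could follow the text and deliver different analyses.

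The shared range is a second, smaller matter. For pain freedom, 30% exceeds both planning rates (22% and 12%). For MBS freedom it is below both (45% and 32%), so even a crossed grid never lets missing placebo subjects respond at the rate planned for placebo subjects generally.

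What is at stake is the robustness statement for a co-primary endpoint, not the principal test.

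**Working it through.** **Inputs.** From SAP Section 5: 380 mITT subjects per arm, planning rates as quoted, alpha 0.0167. The documents give no missing fraction, so m (the fraction missing at 2 hours) is assumed. The 42%/32% result is also assumed, as a significant result smaller than planned.

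**The plan's own figures.** A two-sided chi-square test with 380 per arm gives power of 90.1% for 22% against 12% and 90.3% for 45% against 32%. Both reproduce the stated 90%.

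**Method.** Let rA and rP be the rates imputed for missing active and placebo subjects. If the base rates are NC=F rates, the arm rates after imputation are pA = a + m·rA and pP = b + m·rP. If the base rates are rates among completers, they are pA = (1−m)·a + m·rA and pP = (1−m)·b + m·rP. The test is an unstratified two-sided Wald test with SE = √[pA(1−pA)/380 + pP(1−pP)/380]. Stratification and between-imputation variance are ignored.

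**Step 1: a common rate does not move the difference.** With rA = rP = r and equal m, pA − pP equals a − b (NC=F reading) or (1−m)(a − b) (completer reading) at every r. Only the SE changes. At planning rates with 10% missing per arm, p stays at about 0.001 or less for every r from 0% to 100%.

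**Step 2: what the other analyses assume about missing subjects.** NC=F is the 0%/0% cell. Complete cases gives missing subjects their own arm's completer rate, which for a positive result is higher on active. Copy-from-reference gives both arms about the placebo completer rate. None puts missing active below missing placebo.

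**Step 3: NC=F result 42%/32%, equal missingness.**

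| Analysis | p, 10% missing | p, 5% missing |
|---|---|---|
| NC=F | 0.0041 | 0.0041 |
| Complete cases | 0.0030 (46.7% vs 35.6%, n = 342 per arm) | 0.0035 |
| Copy-from-reference | 0.0048 | 0.0044 |
| Common rate, 0% to 30% | 0.0041 to 0.0047 | 0.0041 to 0.0044 |
| Crossed, active 0% / placebo 30% | **0.0468** | 0.0153 |
| Crossed, active 0% / placebo 40% | not needed, already above 0.0167 | **0.0226** |

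For the 0.0468 entry: pA = 0.42, pP = 0.32 + 0.10 × 0.30 = 0.35, difference 0.07, SE 0.0352, z = 1.99. At 10% missing, crossing decides whether the fragility is seen. At 5% missing, the 30% maximum decides it.

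**Step 4: where the maximum matters once rates are crossed.** The smallest m giving p ≥ 0.0167 with active imputed at 0%:

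| Base rates | placebo 30% | placebo 60% | placebo 100% |
|---|---|---|---|
| 42/32, NC=F | 5.4% | 2.7% | 1.6% |
| 45/32, NC=F | 15.0% | 7.5% | 4.5% |
| 45/32, completers | 10.9% | 6.3% | 4.0% |

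Between the 60% and 30% columns, a crossed grid stopping at 30% misses a tipping point that a grid to 60% would show. Above the 30% column, the existing range already tips once crossed. Below the 100% column, no placebo rate tips the result.

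**The case against.** The strongest reply is that rates assigned group by group naturally suggest arm-specific rates. A common rate would test almost nothing under equal missingness, so it is the less sensible reading, and the separate table templates may already show a crossed layout. That is fair: this is an ambiguity, not a demonstrated omission. But the templates are outside the SAP, and a rule that decides which analyses are run belongs in the pre-specified text.

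It can also be said that 0% to 30% is a defensible range, since subjects who miss the 2-hour entry need not respond above the placebo rate. This largely stands. The step from 30% to 32% is small: at planning rates read as NC=F rates, 10% missing and active at 0%, p is 0.005 at placebo 30% and 0.006 at 32%. The range is the lesser half of the point.

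A reader might infer that the 30% maximum also hides fragility without crossing, when more data are missing on placebo. With 3% missing on active, 8% on placebo and NC=F 42%/32%, a common rate gives p = 0.016 at 30% and 0.023 at 40%. The documents do not support the inference: the planned complete-case analysis (43.3% against 34.8%) gives 0.0188 and copy-from-reference gives 0.0191, so the plan already exposes that case.

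Finally, the missing fractions are assumed. That also stands. Missing MBS at onset and early rescue use are classed as failures before imputation, which limits how many subjects are imputed. SAP 6.3.2 tabulates missing 2-hour symptom data by arm, so the actual fraction will be reported.

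**Conclusion.** The point holds as an inexpensive improvement to a supportive analysis. Its main part is that neither co-primary section states whether imputed rates are crossed, and only a crossed grid tests missing active subjects doing worse than missing placebo subjects. In the assumed case (42%/32%, 10% missing per arm), that choice separates p of 0.005 or less from p = 0.047.

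Its secondary part is the MBS maximum of 30%. Compared with a grid to 60%, it hides a tipping point at about 2.7% to 5.4% missing for 42%/32%. For 45%/32% the range is about 6% to 15%, depending on whether the planning rates are read as completer rates (6.3% to 10.9%) or NC=F rates (7.5% to 15.0%). Outside those ranges, extending to 60% changes nothing about whether a tip is seen.

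A reader might go further and infer that the primary conclusion or its error control is affected. It is not: the NC=F test, alpha, hierarchy and sample size do not depend on this analysis. All sizes rest on assumed, equal missingness and an unstratified approximation.

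**What to change.** In SAP 6.3.3.1 and 6.3.3.2, state that the imputed rates for active and placebo are varied independently in a two-way grid. In 6.3.3.2, extend the MBS grid above 45%, for example 0% to 60% in 10-point steps. In both tables, mark the cells where p is 0.0167 or more. Settle this before unblinding, so that the choice of cells cannot look post hoc.

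The cost is a sentence or two of SAP wording and a larger supportive table: 7 x 7 = 49 cells per dose for MBS and 4 x 4 = 16 for pain freedom. No new data are needed.

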# 6.3.4 Secondary Efficacy Endpoints

All secondary efficacy endpoints will be evaluated for mITT subjects, unless specified otherwise.

If the co-primary endpoint tests are both significant for a BHV-3500 treatment group versus placebo, then the secondary endpoints are tested for that BHV-3500 treatment group versus placebo using a hierarchical gate-keeping procedure, with each test in the hierarchy conducted at alpha=0.0167. The endpoints are tested in the order shown in Section 1.2.2.

A by-subject listing of outcomes for pain relief, nausea freedom, phonophobia freedom, photophobia freedom, and return to normal function will be provided for randomized subjects at each time point post-dose. The listing will also include prophylactic migraine medication use at randomization and time to rescue medication start date/time in minutes (see Section 6.3.4.3), as well as nausea status, phonophobia status, photophobia status, and functional disability level at on-study migraine attack onset. Missing data and complete cases will be flagged at each time point for each endpoint. See Section 6.3.5.2 for efficacy outcomes over time.

#### 6.3.4.1 Pain Relief at 30 Minutes, 60 Minutes and at 2 Hours Post-Dose

Pain relief is defined as a pain level of none or mild at a single time point post-dose.

Pain relief outcomes at 2 hours post-dose will be summarized by treatment group (see Section 6.5.3.2).

At each time point post-dose (30 minutes, 60 minutes, and 2 hours), treatment group comparisons of the percentage of subjects with pain relief will use analogous methods as the principal analysis of the co-primary endpoint of pain freedom with NC=F and RM=F (see Section 6.3.3.1).

## 6.3.4.2 Return to Normal Function at 30 Minutes, 60 Minutes, and 2 Hours Post-Dose

Return to normal function is defined as a functional disability level of normal at a single time point post-dose for subjects with functional disability (mildly impaired, severely impaired, requires bedrest) at on-study migraine attack onset. Thus, all analyses of return to normal function will be based on mITT subjects with functional disability at on-study migraine attack onset.

Return to normal function outcomes at 2 hours post-dose will be summarized by treatment group (see Section 6.3.5.2).

At each time point post-dose (30 minutes, 60 minutes, and 2 hours), treatment group comparisons of the percentage of subjects with return to normal function will use analogous methods as the principal analysis of the co-primary endpoint of pain freedom with NC=F and RM=F (see Section 6.3.3.1).

# 6.3.4.3 Probability of Rescue Medication Use within 24 Hours Post-Dose

Analyses will be based on evaluable mITT subjects, i.e., mITT subjects with rescue medication start date on or before study drug start date + 1 day and missing rescue medication start time will be excluded. Time to rescue medication use will be measured from the study drug start date/time to the rescue medication start date/time.

No analysis window around the 24-hour post-dose time point will be used.

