¹ Screening Phase will be 3 - 28 days. Subject should be entered in the IWRS once they sign the informed consent form to obtain their study subject identification code.

²The **Baseline**/ **Randomization Visit** may only occur *after* all screening procedures are completed and the subject meets all inclusion/exclusion criteria. If the subject does not meet all eligibility requirements, the subject should be screen failed in the IWRS.

³ Subjects will use their assigned eCOA handheld device to answer questions about their migraine symptoms upon experiencing a moderate or severe migraine headache. The subject will administer study drug or matching placebo if the following criteria are met: 1) the headache remains moderate or severe; 2) the subject has completed all required migraine assessment questions in the handheld, including their current most bothersome migraine symptom, and 3) the subject has not already taken prohibited medications (see protocol section 5.4).

⁴ Subjects should keep track of their concomitant and rescue medications on the appropriate study paper diary provided throughout the study. These diaries should be returned to the investigational site for review and electronic data capture (EDC) entry.

⁵ The randomization visit is considered day 1 out of the 45 days subjects have to treat and report a migraine in their handheld device. Subjects will be randomized in the IWRS and will be stratified by answering "yes" or "no" to prophylactic migraine medication use in the IWRS.

⁶Nasal inspection – The nasal passages and turbinates will be visually inspected with a nasal speculum or otoscope at the screening, baseline and end of treatment visits to detect evidence of nasal inflammation or edema.

⁷ Height will only be captured at the Screening Visit. Weight, body temperature, respiratory rate, blood pressure and heart rate will be collected at all time points where indicated. Sitting arterial systolic and diastolic blood pressure and pulse rate will be measured.

- ⁸ SAEs are reported from the time of signed informed consent and non-serious AEs are reported from baseline. All ongoing non-serious AEs and SAEs will be followed to resolution or until the Investigator deems there will be no further status change. SAEs that occur during the treatment period should be reported to site in real time. Non-serious AEs that occur during the treatment period should be reported to the site at the EOT.

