5.4.1 Rescue Medications

After dosing with study medication, all other headache medication is prohibited during the first 2 hours post dose of study drug administration. A subject who does not experience relief of their migraine headache at the end of 2 hours after dosing with study medication (and after the two hour assessments have been completed on the handheld device), will be permitted to use ONLY the following rescue medication: aspirin, ibuprofen, acetaminophen up to 1000mg/day (this includes Excedrin Migraine) Naprosyn (or any other type of non- steroidal anti-inflammatory (NSAID)), antiemetics (e.g., metoclopramide or promethazine), or baclofen. These are the only medications allowed for rescue treatment after 2 hours post dose of study medication.

If the migraine is relieved by study medication at 2 hours after dosing but then returns to a moderate or severe intensity level between 2 and 48 hours, the subject will be permitted to take the same rescue therapy as outlined above.

If needed, 48-hours after dosing with the study medication (and before returning to the clinical site for the End of Treatment Visit), the subject may take their prescribed standard of care medications for treatment of migraine (including triptans if not contraindicated), provided all of the assessments have been completed on the handheld.

In all circumstances, the subject will always continue to complete the handheld entries through the 48-hour assessment after taking the study medication. Use of concomitant medication after randomization, including rescue medication, will be recorded by the subject on a paper diary and returned to the site. The site will record medications that were taken within 14 days of dosing with study medication (or until the End of Treatment Visit) in the EDC.

During the 45 days of the treatment phase, if the subject has a nonqualifying migraine (mild migraine) or a migraine that they do not treat with study medication, the subject is permitted to use only the following medications: aspirin, ibuprofen, Naprosyn (or any other type of non-steroidal anti-inflammatory (NSAID)), antiemetics (e.g., metoclopramide or promethazine), or baclofen.

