# 6.1.2 Type I Error Control

Type I error will be controlled by a hierarchical gate-keeping procedure. First, the family of two co-primary endpoints will be tested. In particular, each BHV-3500 treatment group will be tested for superiority against placebo at a Bonferroni corrected alpha=0.0167 level for both co-primary endpoints. If both co-primary endpoint tests are determined to be significant for a BHV-3500 treatment group versus placebo, then the secondary endpoints will be tested for that BHV-3500 treatment group versus placebo using a hierarchical gate-keeping procedure, with each test in the hierarchy conducted at alpha=0.0167.

The secondary endpoints will be tested in the order shown in Section 1.2.2.

If a test in the hierarchy is not significant, then any further tests on endpoints in the sequence will have p-values presented only for descriptive purposes, and no conclusions will be drawn from those results.

For exploratory endpoints, no attempt will be made to adjust for multiplicity. Any exploratory endpoints for which p-values are produced will be evaluated at an unadjusted two-sided alpha level of 0.05 and presented only for descriptive purposes.

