# 6.2.5.2 Non-Study Medications

Non-study medications will be summarized by therapeutic class and preferred name in descending order of overall frequency. For each subject, multiple records of the same medication will be counted only once within each therapeutic class and preferred name. Imputed medication start and stop dates will be used to assign non-study medication type (prior or concomitant) to all non-study medications except rescue medications. See Section 7.6.2 for details on non-study medication start and stop date imputation, and definitions of non-study medication types.

The following non-study medications will be summarized by as-treated treatment group and All BHV-3500 for treated subjects:

- Prior medications, including results for overall treatment group: all; prophylactic migraine
- Current medications, including results for overall treatment group: all; prophylactic migraine
- Concomitant medications: all; prophylactic migraine
- Rescue medications.

Rescue medications will also be summarized by as-randomized treatment group for mITT subjects to support efficacy.

A by-subject listing of non-study medications will be provided by therapeutic class and preferred name for enrolled subjects. Prophylactic migraine and rescue medications will be identified, as well as medication type.

A by-subject listing of rescue medications will be provided by therapeutic class and preferred name for treated subjects.

Non-study medications will be identified from the Concomitant Medication and Rescue Medication CRFs.

Prophylactic migraine medications are defined as those with a "yes" response to the question about prophylactic migraine medication on the Concomitant Medication CRF.

Rescue medications are defined as non-study medications reported on the Rescue Medication CRF with complete medication dates, and either (1) medication date/time after the study drug start date/time, or (2) medication date at or after study drug start date if the medication time or study drug start time is missing. Rescue medication dates will not be imputed. Rescue medication times will not be imputed, unless specified otherwise (see Section 6.3.5.2).

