# 6.3.1 Principal Analysis Methods of Handling Missing Data and Intercurrent Events

Methods of handling missing data in principal analyses of binary efficacy endpoints are defined as follows:

- Non-Completer = Failure (NC=F): Subjects with missing data at a single time point will be classified as failures. This missing data imputation method will be applied to endpoints based on data from a single time point (e.g., co-primary endpoints at 2 hours post-dose).
- Non-Completer With Missing Data at More Than 1 Time Point = Failure (NC1=F): Subjects with missing data at > 1 time point post-dose in a specified time period will be classified as failures. This missing data imputation method will be applied to endpoints that are based on data from multiple time points (e.g., secondary endpoint of sustained pain freedom from 2 to 24 hours post-dose).
- Non-Completer = Missing (NC=M): Subjects with missing data at a single time point will be excluded from the analysis. This missing data exclusion method will be applied to endpoints based on data from a single time point (e.g., co-primary endpoints at 2 hours post-dose).

The intercurrent event of rescue medication use will be handled using Rescue Medication = Failure (RM=F), i.e., subjects who take rescue medication will be classified as failures for all efficacy evaluations that are reported at or after taking rescue medication, i.e., (1) rescue medication start date/time  $\leq$  eDiary finding date/time if start time is not missing, or (2) rescue medication start date  $\leq$  eDiary finding date if start time is missing; see Sections 6.2.5.2 and 7.3). This method will apply to all efficacy analyses, except the secondary endpoint of rescue medication use within 24 hours post-dose.

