#### **Rescue Medication Use Within 24 Hours Post-Dose**

Rescue medication use within 24 hours post-dose is defined as time to rescue medication use  $\leq$  24 hours.

Treatment group comparisons of the percentage of subjects using rescue medication within 24 hours post-dose will use analogous methods as the principal analysis of the co-primary endpoint of pain freedom, except that the NC=F and RM=F methods will not be applied because they are not applicable to this endpoint (see Section 6.3.3.1).

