## 7.3 Derived Dates

Derived dates are defined as follows:

- Study drug start date/time: Earliest study medication date and time from the eDiary Migraine Report or Study Medication Intake Report (see Section 7.6.3.1). This date is used to define analysis periods.
  - o eDiary Migraine Report
    - If the subject answered "yes" to taking study medication mistakenly already, then the following conventions will be applied depending when drug was reported taken:
      - Today: study drug start date will be set to the finding date, and the study drug start time will be set to the time of study medication taken, if available.
      - Yesterday: study drug start date will be set to the finding date -1 day, and study drug start time will be set to the time of study medication taken, if available.
      - Other: study drug start date will be set to the date of study medication taken, if available.
    - Otherwise, if the subject answered "no" to taking study medication mistakenly already and answered "yes" to confirming having taken study medication, then the study drug start date/time will be set to the finding date/time.
  - o Study Medication Intake Report: Study medication date/time.
- Rescue medication start date/time: Earliest rescue medication date/time (see Section 6.2.5.2). Missing time is considered to be earlier than non-missing time on the same date.
- Imputed rescue medication start date/time: This will be used only for time-to-event efficacy analyses in Section 6.3.5.2, and not for time to rescue medication use analyses in Section 6.3.4.3.
  - o If the rescue medication start date and time are both not missing, then the imputed rescue medication start date/time will be set to the rescue medication start date/time.
  - If the rescue medication start time is missing and the rescue medication start date is
    equal to the study drug start date, then the imputed rescue medication start date/time will
    be set to the study drug start date/time.
  - Otherwise, if the rescue medication start time is missing and the rescue medication start date is equal to a post-dose eDiary finding date with non-missing efficacy data, then the imputed rescue medication start date/time will be set to the first eDiary finding date/time corresponding to non-missing efficacy data.
  - Otherwise, if the rescue medication start time is missing and rescue medication start date is equal to the study drug start date + 1 day, then the imputed rescue medication start

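### The 24-hour rescue analysis drops subjects with an untimed rescue record on the dosing date, although the SAP's own definitions already make them 24-hour rescue users

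*SAP*

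**What the plan says.** SAP 6.3.4.3 limits the analysis to evaluable mITT subjects: those with a "rescue medication start date on or before study drug start date + 1 day and missing rescue medication start time will be excluded". The Revision History lists this as a specific change and gives no reason. The event itself is binary: "Rescue medication use within 24 hours post-dose is defined as time to rescue medication use" of no more than 24 hours.

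Three other SAP rules bear on an untimed record:

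- **6.2.5.2** decides what counts as rescue medication. One of its two routes is a "medication date at or after study drug start date if the medication time or study drug start time is missing", so an untimed record from the dosing date qualifies.
- **6.3.1** (RM=F) falls back on dates for the other efficacy endpoints, comparing the rescue date with the "eDiary finding date if start time is missing".
- **7.3** takes the earliest rescue record and adds: "Missing time is considered to be earlier than non-missing time on the same date". It also has an imputed rescue time, set to the dosing time for untimed dosing-date records, but bars its use in 6.3.4.3.

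SAP 1.2.2 lists rescue use third among 15 secondary objectives, tested in that order. Under 6.1.2, once a test fails, "any further tests on endpoints in the sequence will have p-values presented only for descriptive purposes". SAP 6.1.1 plans missing-data sensitivity analyses for the co-primary and exploratory efficacy endpoints, not for this one.

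**The concern.** The exclusion covers two different situations with one rule. An untimed next-day record leaves the 24-hour status open, whereas an untimed dosing-date record does not. The same record counts the subject as a failure for sustained pain relief to 24 hours, yet removes that subject from the endpoint that measures rescue use over those hours.

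A second group is lost through 7.3. A subject with a timed use within 24 hours on the next day, plus an untimed record on that same date, has the untimed record ranked first and is excluded despite a documented event.

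A subject without a rescue record can never be excluded, so selection depends on the outcome. If those removed are true users, the rescue rate is understated in each arm. If the share of missing times differs by arm, the treatment difference is biased, in either direction. A missed result here makes 12 later tests (15 − 3) descriptive for that dose. The co-primary tests are not affected.

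**Working it through.** **The plan's own power figure.** Inputs from SAP section 5: 380 per arm, alpha 0.0167. A two-sided pooled-variance two-proportion test gives 90.1% for 22% v 12% and 90.3% for 45% v 32%, and 0.901 × 0.903 = 81.4% jointly. The stated 90%, 90% and roughly 80% reproduce, so the same test is used below. The plan states no figure for the rescue endpoint.

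**Elapsed time.**

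- Dosing date: the longest gap is dosing at 00:00 and rescue at 23:59, which is 1,439 minutes. This is under 1,440, so the event definition is always met.
- Next day: the gap runs from 1 minute to 47 h 59 min, so the status is indeterminate without a time.

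**Size. All rates here are assumptions, not document figures.** Let

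- p = true 24-hour rescue rate, 40% placebo and 30% active;
- m = share of true users whose earliest record is untimed;
- d = share of those records dated on the dosing date;
- f = share of true users among subjects excluded for a next-day record only;
- g = share of untimed dosing-date subjects who are non-users with a pre-dose intake.

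Then dd = m·p·d, nd = m·p·(1 − d), k = nd·(1 − f)/f and c = dd·g/(1 − g).

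- SAP rule: rate = (p − dd − nd)/(1 − dd − nd − k − c)
- Fix: rate = (p − nd + c)/(1 − nd − k)
- Bounds with c = 0: p + k (next-day all events) and p − nd (all non-events)
- n per arm = 380 × the retained fraction (the denominator)

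Full data, 40% v 30%: the null standard error is √(0.35 × 0.65 × 2/380) = 0.0346, the alternative standard error is √((0.24 + 0.21)/380) = 0.0344, and the critical value is 2.393. Power = Φ((0.10 − 2.393 × 0.0346)/0.0344) = 69%.

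*1. All untimed records on the dosing date, all true users (d = 1, g = 0).* At m = 10%: (0.40 − 0.04)/(1 − 0.04) = 37.5% and (0.30 − 0.03)/(1 − 0.03) = 27.8%.

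| Untimed share of users | SAP rule: placebo v active | Difference (points) | Power |
|---|---|---|---|
| 2% both arms | 39.5% v 29.6% | 9.9 | 68% |
| 5% both arms | 38.8% v 28.9% | 9.8 | 67% |
| 10% both arms | 37.5% v 27.8% | 9.7 | 66% |
| 12% placebo, 8% active | 37.0% v 28.3% | 8.7 | 55% |
| 8% placebo, 12% active | 38.0% v 27.4% | 10.6 | 75% |

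The fix returns 40% v 30%, 10.0 points and 69% in every row. With no true effect (40% in both arms), shares of 12% v 8% give a false difference of 1.0 point and 2.1% rejection instead of 1.67%. Equal shares under no effect give no bias.

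*2. Mixed dates (m = 10%, d = 0.5, f = 0.5).* SAP rule: 38.3% v 28.3%, 10.0 points, 68%. Fix: 39.6% v 29.4%, 10.2 points, 70%. Bounds: 10.5 and 9.5 points. The fix brings the arm rates nearer the truth but not the difference, because the SAP rule's errors cancel.

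*3. Some pre-dose intake (m = 10%, d = 1).* At g = 10% the fix gives 10.1 points and the SAP rule 9.7. At g = 25% they give 10.3 and 9.9. Above about g = 16% the SAP difference is the nearer to 10.

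**The case against.** The rule was written on purpose, and the authors chose not to use the imputed times here. SAP 6.2.5.2 and RM=F settle an ambiguous record by convention; they do not show that the intake followed dosing. Protocol 5.4.1 permits some medication "if the subject has a nonqualifying migraine (mild migraine) or a migraine that they do not treat with study medication", so an untimed same-day intake may have come before the study drug. Counting doubtful rescue as failure is natural when rescue is an intercurrent event, and less obviously so when it is the outcome.

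Nor does the fix always improve the treatment difference. With one non-user per next-day user, m of 2%, 5% or 10% and d of 25% or 50%, the current rule is nearer the true difference in all six combinations. At d = 75% the fix is nearer, by at most about 0.06 points. The larger effects need 12% v 8% untimed, and nothing in a double-blind trial with identical-looking products suggests such a gap. At 2.4% v 1.6% with no true effect, the false difference is 0.2 points and rejection stays about 1.7%. Missing times may also be rare. On the paper diaries, Protocol Table 1 footnote 4 says: "These diaries should be returned to the investigational site for review and electronic data capture (EDC) entry".

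Finally, the fix still excludes some subjects because they have a rescue record, and it gives the binary and Kaplan-Meier analyses different denominators.

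All of this stands as a limit on the size and on the promised gain. None of it gives a reason to remove, from a yes/no endpoint, subjects whose status the SAP's definitions settle, or subjects with a timed use within 24 hours. The Kaplan-Meier analysis needs a clock time; the binary test in the hierarchy does not.

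**Conclusion.** The concern holds and is minor. The classification argument is firm: given the 6.2.5.2 definition, an untimed dosing-date record is always a 24-hour event. The practical effect is uncertain and probably small. With equal untimed shares of 2% to 10%, the assumed 10-point difference shrinks by at most about 0.3 points and power by about 3 percentage points. Only unequal shares by arm cause material bias, and the documents neither suggest nor rule them out. The case for changing the rule rests on consistent classification and on removing most of an outcome-dependent exclusion, not on a guaranteed gain in power or in accuracy of the difference. Excluding subjects whose only evidence is an untimed next-day record is defensible and is not criticised.

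**What to change.** In the binary 24-hour analysis, count as events:

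- any record dated on the study-drug start date that meets the SAP 6.2.5.2 rescue definition, timed or not;
- any timed record at or before 24 hours, even when another record is untimed.

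Keep the exclusion only for subjects whose sole qualifying evidence is an untimed next-day record. For these, add two bounding sensitivity analyses: all as events, then all as non-events. Keep the current rule as a further sensitivity run, which covers possible pre-dose intake. Report the number of untimed records per arm, split by dosing date and next day. Leave the Kaplan-Meier analysis as written, do not place untimed records at time zero, and footnote that its denominator differs.

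The cost is SAP wording, one derivation and a few sensitivity rows, with no new data. The downside is that an untimed dosing-date intake that in fact preceded dosing would count as an event, as 6.2.5.2 already treats it. The change should be made before unblinding, so that it cannot appear to follow the arm-level counts.
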